**Figure 1. Schema for Study GPIH.**

### Visit 1

Interested individuals will sign the informed consent form prior to initiating any procedure.

The investigator will review medical history and other inclusion and exclusion criteria prior to any diagnostic procedures.

### Visit 2

The investigator will review the results of the screening laboratory measures to further assess participant eligibility.

For participants meeting all other eligibility requirements, a dilated fundoscopic examination will be scheduled and completed between Visit 2 and Visit 3.

Participants or caregivers, if applicable, will receive a blood glucose (BG) meter and clinical outcome assessment device.

Participants will be asked to monitor 7-point self-monitoring of BG profiles (prior to and 2 hours after the 3 main meals and at bedtime) on 2 nonconsecutive days during the 2 weeks preceding prespecified visits.

Participants should continue their diet and exercise routine and must not use any glucose-lowering treatment other than the OAM taken prior to the screening visit and should not change their dose or formulation.

**Period II: treatment period*****Visit 3 (Randomization)***

All screening laboratory test results and screening dilated fundoscopic examination results must be reviewed for exclusion criteria prior to randomization and dosing at Visit 3.

This is the general flow for Visit 3:

- Participants arrive to the clinic in the fasting state.
- Study personnel confirm enrollment criteria.
- Participants are randomly assigned to an intervention group.
- Participants complete patient-reported outcome questionnaires before any other study procedures if the participant is not adversely affected by the fasting condition or complete after the participant has sufficiently recovered.
- Study personnel complete all required visit procedures, including the collection of vital signs, all baseline procedures, sample collection, and dispense study intervention.
- Participants self-administer study intervention at home. Administration should occur on the day ( $\pm 3$  days) of when the next dulaglutide administration is planned

***Visit 4 through Visit 10***

Participants complete all visit procedures described in the schedule of activities.

***Visit 11 or early discontinuation visit***

Participants unable or unwilling to continue the study for any reason will perform an early discontinuation (ED) visit. If the participant is discontinuing during an unscheduled visit or a scheduled visit, that visit should be performed as the ED visit.

**Period III: safety follow-up visit*****Visit 801***

All participants who complete the treatment period or discontinue the study early (ED) are required to complete Visit 801, a safety follow-up visit, approximately 4 weeks after their last treatment or ED visit.

**Method of treatment assignment**

Participants who meet all entry criteria for enrollment will be centrally assigned to 1 of the study treatments arms at Visit 3. Assignment to treatment arms will be determined by a computer-generated random sequence using an interactive web-response system (IWRS).

Participants will be randomly assigned in a 1:1 ratio to tirzepatide or dose escalation of dulaglutide.

Participants will be stratified based on

- starting dulaglutide dose at screening (0.75 mg, 1.5 mg)
- region (North America, European Union)
- number of OAMs (0 to 1 or 2 to 3), and
- HbA1c ( $\leq 8.5\%$  or  $> 8.5\%$ ).

## 2. Statistical Hypotheses

The null hypothesis corresponding to the primary objective of this study is as follows:

- **H1,0** - Switching from dulaglutide to 15 mg or MTD of tirzepatide is not superior to continuing and escalating to dulaglutide 4.5 mg or MTD with respect to HbA1c mean change from baseline at Week 40 in participants who entered the study on a nonmaximal dose of dulaglutide.

The null hypothesis corresponding to the key secondary objective is as follows:

- **H2,0** – Switching from dulaglutide to 15 mg or MTD of tirzepatide is not superior to continuing and escalating to dulaglutide 4.5 mg or MTD with respect to weight mean change from baseline at Week 40 in participants who entered the study on a nonmaximal dose of dulaglutide.

Operationally the hypotheses will be evaluated by 2-sided tests.

### 2.1. Multiplicity Adjustment

The primary and the key secondary objectives will be evaluated using both the treatment-regimen and the efficacy estimands. Since the purpose for each estimand is different, multiplicity adjustment will be conducted for each estimand separately.

The statistical comparisons for the primary efficacy endpoint and the key secondary endpoint will be carried out in the hierarchical order. This means that statistically significant results for the comparison in the higher rank (primary) is required to initiate the testing of the next comparison in the lower rank (key secondary). Since a fixed sequence testing is used, each comparison will be tested at a significance level of 1-sided 0.025, and an overall alpha level of 1-sided 0.025 will be preserved (Westfall and Krishen, 2001).

### 3. Analysis Sets

This table defines the analysis populations and datasets for the purposes of analysis based on the estimands defined in Section 1.1.

Population/Analysis Set	Description
Screened population	All participants who signed informed consent
Randomized population	All participants who are randomly assigned to a treatment arm
Modified intent-to-treat population (mITT)	All randomly assigned participants who are exposed to at least 1 dose of study intervention. Participants will be analyzed according to the treatment they were randomly assigned to regardless of the treatment actually received.
Efficacy Analysis Set (EAS): This analysis set will be used to estimate the efficacy estimand for the primary and key secondary objectives	Data obtained during the treatment period from the mITT population excluding patients who were inadvertently enrolled, excluding data after permanent discontinuation of treatment or initiation of antihyperglycemic rescue medication or prohibited medication
Full Analysis Set (FAS): This analysis set will be used to estimate the treatment-regimen estimand for the primary and key secondary objectives	Data obtained during the treatment period from the mITT population excluding patients who were inadvertently enrolled, regardless of adherence to treatment or initiation of antihyperglycemic rescue medication or prohibited medication (excluding nonstudy tirzepatide or dulaglutide). Data after taking nonstudy tirzepatide or dulaglutide will be excluded.
Safety Analysis Set (SS): This analysis will be used to assess the safety of study treatment	Data obtained during the treatment period plus safety follow-up from the mITT population, regardless of adherence to treatment or initiation of rescue antihyperglycemic medication or prohibited medication.

## 4. Statistical Analyses

### 4.1. General Considerations

Statistical analysis of this study will be the responsibility of Lilly or its designee. The statistical analyses will be performed using SAS® Version 9.4 or higher.

Any change to the data analysis methods described in the protocol will require an amendment ONLY if it changes a principal feature of the protocol. Any other change to the data analysis methods described in the protocol, and the justification for making the change, will be described in the SAP or clinical study report (CSR). Some analyses and summaries described in this analysis plan may not be conducted if not warranted by data (for example, too few events to justify conducting an analysis). Listings of events will be provided in such situations. Additional exploratory analyses of the data will be conducted as deemed appropriate without further changes made to the protocol or SAP, even after final database lock.

All tests of treatment effects will be conducted at a 2-sided alpha level of 0.05/1-sided alpha level of 0.025, unless otherwise stated, and all confidence intervals (CIs) will be given at a 2-sided (95%) level. In statistical summaries and analyses, all data will be analyzed by randomly assigned treatment assignment. Participants will be analyzed according to the treatment they were randomly assigned to, regardless of the treatment actually received.

Baseline is defined as the last nonmissing measurement recorded on or before the randomization visit, prior to first dose of treatment, unless otherwise specified. For laboratory values, baseline needs to be prior the first dose time.

Efficacy analyses will use the Efficacy Analysis Set (EAS) to evaluate the efficacy estimand and the Full Analysis Set (FAS) to evaluate the treatment-regimen estimand. Safety will be assessed using Safety Analysis Set (SS). Selected safety analyses may be conducted after excluding data on rescue therapy or data after starting another antihyperglycemic medication.

End of study participation for a patient will be the earliest of date of death, date of withdrawal from further participation in the study, or date of safety follow-up visit (Visit 801). For patients considered to be lost to follow-up, end of study participation will be the date of lost to follow-up reported by the investigator. Patient data included in the database after the last date of study participation (earliest of date of death, date of ED or date of safety follow-up) will be excluded from statistical analysis. Listings of such data may be provided.

Summary statistics for continuous measures may include sample size, mean, standard deviation, median, minimum, and maximum. The analysis model to make comparisons between treatment groups relative to continuous measurements assessed for specific time will be an analysis of covariance (ANCOVA) and for over time will be mixed-effects model for repeated measures (MMRM).

The Kaplan-Meier method will be used for estimation of cumulative event-free survival rates over time, and Cox proportional hazards regression analysis will be used to compare hazard rates among treatments.

Summary statistics for categorical measures, including categorized continuous measures, will include sample size, frequency, and percentages. Logistic regression will be used to examine the treatment difference in binary efficacy outcomes when 1 or more covariates are included in the model. Otherwise, Fisher's exact test will be used. The negative binomial regression model will be used for the treatment comparison of discrete count measures if deemed appropriate.

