9.3.5.4. Central Laboratory Measures and Vital signs

Values and change from baseline to postbaseline values of central laboratory measures and vital signs will be summarized at each scheduled visit.

The analysis model to make comparisons between treatment arms relative to continuous change from baseline values assessed over time will be an MMRM, with terms: treatment, visit, and treatment-by-visit interaction, number of background OAMs (0-1, 2-3), dulaglutide dose at screening, region, and baseline measurement as covariates.

An unstructured covariance structure will model relationship of within-participant errors.

The percentages of participants with treatment-emergent abnormal, high, or low laboratory measures at any time will be summarized and compared between treatment groups by using Fisher's exact test.

A treatment-emergent abnormal value is defined as a change from normal value at baseline to an abnormal value at any time during the follow-up. A treatment-emergent high result is defined as a change from a value less than or equal to the high limit at baseline to a value greater than the high limit at any time during the Treatment and Follow-up Periods. A treatment-emergent low result is defined as a change from a value greater than or equal to the low limit at baseline to a value less than the low limit at any time during the Treatment and Follow-up Periods. High and low limits will be provided in the SAP.

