#### 4.6. Safety Analyses

Safety assessments will be done using the SS (See Section 3) irrespective of adherence to study intervention or initiation of rescue antihyperglycemic medication or prohibited medication, unless indicated otherwise. AEs will be coded from the actual term using the Medical Dictionary for Regulatory Activities (MedDRA) and reported with Preferred Terms (PTs) and System Organ Class (SOC). Selected notable AEs of interest may be reported using High-Level Terms (HLTs) or Standardized MedDRA Queries (SMQs). Summary statistics will be provided for incidence of treatment-emergent AEs (TEAEs), serious AEs (SAEs), and study discontinuation due to AEs, study intervention discontinuation due to AEs, or deaths from the time of first dose through the end of safety follow-up. Counts and proportions of participants experiencing AEs will be reported for each treatment group, and Fisher’s exact test will be used to compare the treatment groups.

Where necessary, for selected continuous safety parameters, the mean change from baseline at Week 40 will be assessed via MMRM using REML. Data from scheduled visits will be utilized for this analysis unless specified otherwise. The model for the analysis during the 40-week treatment period will include treatment, visit, treatment-by-visit interaction, number of background OAMs (0 to 1, 2 to 3), dulaglutide dose at screening, and region as fixed effects, and baseline value of the safety parameter as a covariate. To model the covariance structure within participants, the unstructured covariance matrix will be used. If this model fails to converge, the covariance structures specified in Section [4.3.2](#) will be tested in order until met convergence. If the data does not warrant the MMRM model, then ANCOVA model will be conducted. Where

necessary, the rate of events will be analyzed using a generalized linear MMRM assuming the number of events follow a negative binomial distribution and with treatment as a fixed effect.

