#### **4.9. Changes to Protocol-Planned Analyses**

The only change to the protocol planned analyses that is proposed in the SAP is related to the description of the analyses data sets in Section 3. In this section, it is clarified that data after taking nonstudy tirzepatide or dulaglutide will be excluded from the FAS.

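### The SAP's data cut-off at the date of ED removes the safety follow-up of participants who leave the study early, against its own safety window

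*SAP*

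**What the plan says.** SAP 4.1 gives two end dates in one paragraph. The opening sentence reads "End of study participation for a patient will be the earliest of date of death, date of withdrawal from further participation in the study", or the date of Visit 801, and a separate sentence covers loss to follow-up. The paragraph then removes data recorded after the last date of participation, this time defined as the "earliest of date of death, date of ED or date of safety follow-up) will be excluded from statistical analysis". Listings of the removed data are optional.

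SAP 1.2 ties ED to leaving the study: "Participants unable or unwilling to continue the study for any reason will perform an early discontinuation (ED) visit". It then requires further follow-up of the same people: "All participants who complete the treatment period or discontinue the study early (ED) are required to complete Visit 801", about 4 weeks after the last treatment or the ED visit. Protocol 4.1.1 has the same rule.

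The safety window is stated elsewhere:

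- SAP 3, Safety Analysis Set: "Data obtained during the treatment period plus safety follow-up from the mITT population".
- SAP 4.6, safety summaries: these include "study intervention discontinuation due to AEs, or deaths from the time of first dose through the end of safety follow-up". Protocol 9.3.5 gives the same window.
- Protocol 9.3.5.4, treatment-emergent high result: a change "to a value greater than the high limit at any time during the Treatment and Follow-up Periods". The definition of a low result uses the same periods.

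SAP 4.9 says: "The only change to the protocol planned analyses that is proposed in the SAP is related to the description of the analyses data sets". It then describes only the exclusion from the FAS of data after nonstudy tirzepatide or dulaglutide.

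**The concern.** For a participant who leaves the study and then attends Visit 801, the ED date comes before the Visit 801 date. A rule that takes the earliest date therefore stops at ED. The trial collects the follow-up visit and then discards it from the analysis.

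The loss is selective. Completers keep their 4-week follow-up in the incidence tables and Fisher's exact tests, and early leavers do not. Protocol 7.2 lists malignancy (with exceptions), pregnancy and safety reasons among the grounds for leaving, so this group may be enriched for safety-relevant cases. Protocol 2.2 gives tirzepatide a mean half-life of about 5 days, so someone dosed up to ED still has drug exposure during part of the excluded time. If early leaving differs between arms, safety ascertainment would differ too. The documents do not show that it will.

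**Working it through.** The plan states no figure on this point, so the check is a comparison of texts followed by a rough sizing.

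**Which date the rule selects**

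| Participant | Dates available | Earliest | Data after it |
|---|---|---|---|
| Completes treatment, attends Visit 801 | Visit 801 | Visit 801 | None lost |
| Stops treatment only, stays in the study (Protocol 7.1), then Visit 801 | Visit 801 | Visit 801 | None lost |
| Leaves the study, attends Visit 801 | ED, Visit 801 | ED | ED to Visit 801 excluded |
| Leaves the study, dies before Visit 801 | ED, death | ED | Post-ED events, including the death, excluded from the tables |

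The last two rows conflict with SAP 3, SAP 4.6 and Protocol 9.3.5.4, which all extend through follow-up.

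**Could ED mean something else here?** SAP 4.3.1 also uses the term for early discontinuation of study intervention. On that reading the rule would delete the retrieved-dropout data on which the treatment-regimen imputation depends. It would also contradict the FAS definition, which keeps data regardless of adherence. The study-discontinuation reading is therefore the sensible one, and under it the primary and key secondary analyses are untouched.

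**Size**

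Inputs: 250 randomised (SAP 5), 40 weeks of treatment and 4 weeks of follow-up (SAP 1.2). The share p who leave the study and attend Visit 801 is not given and has to be assumed. SAP 5 mentions a 15% discontinuation rate without saying whether it concerns treatment or study, and Protocol 7.2 expects study discontinuation to be uncommon. I use 5 to 15%, with 15% as an upper value, and add 2% as a low case.

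- Affected participants = 250 × p
- Lost time = 250 × p × 4 weeks
- Planned post-randomisation time = 250 × (40 + 4) = 11,000 person-weeks
- Planned safety follow-up time = 250 × 4 = 1,000 person-weeks

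| p | Participants | Lost person-weeks | Share of 11,000 | Share of 1,000 |
|---|---|---|---|---|
| 2% | 5 | 20 | 0.18% | 2% |
| 5% | 12.5 | 50 | 0.45% | 5% |
| 10% | 25 | 100 | 0.91% | 10% |
| 15% | 37.5 | 150 | 1.36% | 15% |

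Four weeks per person is best read as a maximum. The Schedule of Activities times Visit 801 from the last dose, so someone who stopped dosing before leaving may have a shorter gap.

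For an individual the share is larger. Leaving at week 8, 20 or 32 loses 4/12 = 33%, 4/24 = 17% or 4/36 = 11% of that person's safety observation.

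**The case against.** The best defence is that the parenthesis is loose shorthand. The paragraph's opening sentence ends participation at withdrawal from further participation, and a person who still attends Visit 801 has arguably not withdrawn. On that view the purpose is only to drop stray records dated after a participant is finally gone. The specific safety sections agree with each other, and a programmer following them would keep Visit 801. This is a plausible account of intent. It is not what the sentence says: ED is the term SAP 1.2 applies to people who still owe Visit 801. The consistency of the other sections shows the conflict without resolving it. The opening sentence is not a secure remedy either, because a withdrawal date recorded at the ED visit would cut at the same point.

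The objections about size largely stand. The affected share is unknown, Protocol 7.2 asks for the ED and follow-up visits only where possible and applicable, and the time lost per person may be under 4 weeks.

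There are also real safeguards. Events starting on or before ED are kept. Calcitonin, pancreatic amylase and lipase are scheduled at the ED visit as well. All deaths and SAEs are listed (SAP 4.6.1.1 and 4.6.1.2), and SAP 4.6.1 requires narratives for deaths, SAEs, pregnancies and permanent treatment discontinuations due to AEs. None of these returns post-ED events to the comparative tables.

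**Conclusion.** The concern holds: the cut-off is wrong as written and should be fixed. Applied literally, it removes from the statistical analysis safety data that SAP 3, SAP 4.6 and the protocol say are analysed, and SAP 4.9 does not declare the change. The conclusion rests on reading ED as early discontinuation of the study, as SAP 1.2 uses it.

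The overall quantity is modest and depends on the assumed 5 to 15%. What is chiefly at risk is the tabulated incidence of events after ED, and Visit 801 laboratory and vital-sign values, in a small group that may not be typical. Any imbalance between arms is a possibility, not something the documents establish.

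**What to change.** Use one definition for both end dates in SAP 4.1: the earliest of death, date of loss to follow-up, withdrawal of consent to any further data collection, or Visit 801. Then add two statements:

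- A recorded study-ED or withdrawal date does not cut off a Visit 801 that was attended.
- Data from ED through Visit 801 are included in the Safety Analysis Set.

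As a minor clarification, use separate terms for early discontinuation of the study and of study intervention, since SAP 4.3.1 uses ED for the latter.

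The cost is a few sentences in the SAP. No extra data, visits or participants are needed.

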## 4.2. Participant Dispositions

Reasons for screen failures as reported by investigators will be summarized.

A listing of final study disposition and a listing of randomized treatment assignment (planned treatment) for all randomized patients will be provided. Final study disposition and study treatment disposition for all randomized patients will be summarized by planned study treatment.

The number and percentage of participants prematurely discontinuing study treatment and study prior to the 40-week visit will be provided by study treatment. Reasons for prematurely discontinuing study treatment and study prior to the 40-week visit will be provided by study treatment.

## 4.3. Primary Endpoint Analysis

The primary endpoint for this study is change from baseline in HbA1c to the 40-week visit (Visit 11). This endpoint will be used to evaluate the primary objective of the study for both the treatment regimen and the efficacy estimands (Section 1.1).

The primary efficacy measure will be mean change in HbA1c (percentage and mmol/mol) from baseline (postbaseline to baseline). Both HbA1c values as well as change from baseline in HbA1c will be summarized by treatment and nominal visit (week). If scheduled HbA1c data at the primary endpoint visit are not available, unscheduled HbA1c data collected for the primary endpoint visit will be included in the analysis.

### 4.3.1. Primary Analysis Relative to the Treatment-Regimen Estimand

The primary analysis relative to the treatment-regimen estimand will be conducted utilizing HbA1c data in the FAS at baseline and at the 40-week visit with the aid of an ANCOVA model. ANCOVA model for change from baseline in HbA1c at Week 40 with terms includes treatment (tirzepatide and dulaglutide), number of background OAMs (0 to 1 or 2 to 3), dulaglutide dose at screening (0.75 mg or 1.5 mg), region (North America, European Union) as fixed effect, and baseline HbA1c as a covariate. The ANCOVA analysis will be conducted with multiple imputation of missing primary measure and statistical inference over multiple imputation of missing data guided by Rubin (1987).

For the purpose of the treatment-regimen estimand, missing HbA1c values at the 40-week visit will be imputed based on observed data in the same treatment arm from participants who had their efficacy assessed after ED of study intervention (retrieved dropouts). In cases where there are not enough retrieved dropouts to provide a reliable imputation model (in other words, the model implemented by the SAS program does not converge), an alternative multiple imputation method with reference to the baseline values (return to baseline multiple imputation) will be used

as the primary analysis relative to the treatment-regimen estimand. If value of the imputed HbA1c change from baseline is  $<-6.0\%$  or  $>6.0\%$ , that value will be set to  $-6.0\%$  or  $6.0\%$ , respectively, to avoid unrealistic imputed values.

With the aid of the ANCOVA analysis, p-values, and 2-sided 95% CIs for mean change in HbA1c from baseline to the 40-week visit will be derived and summarized for the tirzepatide 15 mg or MTD arm compared to dulaglutide 4.5 mg or MTD arm.

